#### **6.11.13. Liver Biopsy**

All possible attempts should be made to acquire a liver biopsy specimen of at least 2.0 cm in length to ensure accurate staging of fibrosis and other histological lesions. A historical biopsy within 6 months of the Screening visit may be accepted as the Screening biopsy. The liver biopsy sample must be deemed adequate for evaluation by the central reader for inclusion.

Liver biopsies will be sent to a central laboratory and then will be read by a central reader. The central reader will read all Screening biopsies for eligibility. This assessment will include an assessment of the adequacy of the specimen as well as the fibrosis stage and a determination that the biopsy is consistent with NASH. Histology results from local readers will be collected, if available.

If the liver biopsy is deemed unacceptable by the central reader, it may be repeated. On-treatment liver biopsy results will be blinded to the investigator and subject unless the subject progresses to cirrhosis (F4 fibrosis). CCI

If a liver biopsy is performed per standard of care outside of protocol mandated assessments (e.g., to confirm clinical suspicion of progression to cirrhosis), all possible attempts should be made to submit the biopsy specimen to the central reader for evaluation. If progression to cirrhosis is confirmed by the central reader, the subject will be offered the opportunity to rollover into the OL Phase of the study.

Please refer to the Study Procedures Manual for additional information.

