**Study Procedures Table – Week 60 to Follow Up**

Assessments	On-treatment Visits										Follow Up o	Telephone Follow-Up p
	Week 60	Week 72	Week 84	Week 96	Week 108	Week 120	Week 132	Week 144	Week 156	ET o		
		Week 168	Week 180	Week 192	Week 204	Week 216	Week 228	Week 240 (EOT)				
Physical Examination	X b	X b	X b	X b	X b	X b	X b	X b	X b	X b	X b	
Vital Signs including Body Weight	X	X	X	X	X	X	X	X	X	X	X	
Waist Circumference		X		X		X		X		X		
Liver Biopsy d								X q		X r		
CP/MELD scores e	X	X	X	X	X	X	X	X	X	X		
Assess Ascites and Hepatic Encephalopathy	X	X	X	X	X	X	X	X	X	X		
Abdominal Ultrasound (OL Phase only)		X		X		X		X		X		
Elastography (if available)				X				X		X		
Health Related Quality of Life Questionnaires g		X		X		X		X		X		
Health Resource Utilization Questionnaires g		X		X		X		X		X		
Stool Frequency Assessment	X	X	X	X	X	X	X	X	X	X	X	
Lifestyle Modification Counseling	X	X	X	X	X	X	X	X	X	X		
Adverse Events	X	X	X	X	X	X	X	X	X	X	X	X
Concomitant Medications	X	X	X	X	X	X	X	X	X	X	X	
Dispense Study Drug	X	X	X	X	X	X	X	X s	X			
Review of Study Drug Dosing Compliance (Pill Count)	X	X	X	X	X	X	X	X	X	X		

Assessments	On-treatment Visits										Follow Up o	Telephone Follow-Up p
	Week 60	Week 72	Week 84	Week 96	Week 108	Week 120	Week 132	Week 144	Week 156	ET o		
		Week 168	Week 180	Week 192	Week 204	Week 216	Week 228	Week 240 (EOT)				
Laboratory Assessments												
Subject Fasting	X	X	X	X	X	X	X	X	X	X	X	
Chemistry i , Hematology, Coagulation	X	X	X	X	X	X	X	X	X	X	X	
Insulin and Lipids		X		X		X		X		X		
HbA1c		X		X		X		X		X		
eGFR	X	X	X	X	X	X	X	X	X	X	X	
Pregnancy Testing j	X	X	X	X	X	X	X	X	X	X	X	
Single PK sampling l	X	X	X	X	X	X	X	X	X	X l		
Blood Collection (Biomarkers)				X				X		X		
Urine Collection				X				X		X		
CCI												
Approximate amount of blood drawn (mL) n	12	15	12	65	12	15	12	65	12	65	10	

- a Subjects starting the OL Phase of the study will complete the same study procedures as during the Randomized Phase of the study, starting with the Day 1 visit
- b Symptom-driven PE
- c CP score to be calculated only at Screening
- d Not to be performed during the OL Phase of the study
- e CCI [REDACTED]
- f CCI [REDACTED]

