3.6. Missing Data and Outliers

3.6.1. Missing Data

For missing last dosing date of study drug, imputation rules are described in Section 4.2.1. The handling of missing or incomplete dates for AE onset is described in Section 7.1.5.3, and for prior and concomitant medications in Section 7.4.

The following imputation approaches will be applied to efficacy endpoints as specified:

1) Non-Responder Imputation (NRI)

For purpose of analysis at a defined time point, when NRI is used, all subjects with missing values will be analyzed as not meeting the corresponding endpoint. The NRI method will be applied to subjects with or without baseline value.

2) Multiple Imputation (MI):

The MI procedure replaces each missing data point of the binary primary histology efficacy endpoint (defined in Section 6.1.1) with a set of plausible values that represent the uncertainty about the right value to impute under the missing at random (MAR) assumption. The imputation model used to impute missing data points will be based on the logistic regression with the treatment arms and the 2 stratification factors as covariates. A total of 50 imputed datasets will be generated by the imputation model. That is, each missing data point will be imputed 50 times. Each imputed data set will be analyzed by the method for the primary analysis as specified in Section 6.1.3. The results from these 50 imputed data sets will be combined using Rubin's rule {[Rubin 1987](#)}.

3) Tipping Point Analysis (TPA):

If any significant result in favor of SEL 18 mg or SEL 6 mg is detected in the primary analysis of the binary primary histology efficacy endpoint (described in Section 6.1.3), a delta-adjusting pattern-mixture approach for TPA {[Ratitch 2013](#)} will be conducted to assess the robustness of the primary analysis results under a missing not at random assumption for SEL arms. Specifically, it is assumed that a systematic difference exists between the conditional distributions of the missing and observed data in the SEL arms. To reflect such a systematic difference, a shift parameter δ will be applied to the imputation model (ie, the logistic regression with the treatment arms and the 2 stratifications factors as covariates) when the missing data points in the SEL arms are imputed. For each value of δ , multiply imputed data sets will be generated, each data set will be analyzed by the same method for the primary analysis, and analysis results will then be combined by Rubin's rule. Thus, by

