Baseline/OL-Baseline	1	(none)	1
Week 4/OL-Week 4	29	2	56
Week 12/OL-Week 12	85	57	126
Week 24/OL-Week 24	169	127	252
Week 48/OL-Week 48	337	253	420
Week 72/OL-Week 72	505	421	588
Week 96/OL-Week 96	673	589	756
Week 120/OL-Week 120	841	757	924
Week 144/OL-Week 144	1009	925	1092
Week 168/OL-Week 168	1177	1093	1260
Week 192/OL-Week 192	1345	1261	1428
Week 216/OL-Week 216	1513	1429	1596
Week 240/OL-Week 240	1681	1597	≥1681

Table 3-3. Analysis Visit Windows for ELF test score and components, FibroSure/FibroTest, α -Macroglobin, Haptoglobin, Apolipoprotein A1, C-Reactive Protein (CRP) and Total Bile Acids

Analysis Visit	Nominal Day	Lower Limit	Upper Limit
Baseline/OL-Baseline	1	(none)	1
Week 12/OL-Week 12	85	2	126
Week 24/OL-Week 24	169	127	252
Week 48/OL-Week 48	337	253	420
Week 72/OL-Week 72	505	421	588
Week 96/OL-Week 96	673	589	756
Week 120/OL-Week 120	841	757	924
Week 144/OL-Week 144	1009	925	1092
Week 168/OL-Week 168	1177	1093	1260
Week 192/OL-Week 192	1345	1261	1428
Week 216/OL-Week 216	1513	1429	1596
Week 240/OL-Week 240	1681	1597	≥1681

Table 3-4. Analysis Visit Windows for Elastography and Pooled Cohort Risk and Score

Analysis Visit	Nominal Day	Lower Limit	Upper Limit
Baseline	1	(none)	1 (28*)
Week 24	169	2(29*)	252
Week 48	337	253	420
Week 72	505	421	588
Week 96	673	589	840
Week 144	1009	841	1176
Week 192	1345	1177	1512
Week 240	1681	1513	≥1681

* for Elastography.

Table 3-5. Analysis Visit Windows for Cytokeratin-18 (CK-18) M30 and CK-18 M65

Analysis Visit	Nominal Day	Lower Limit	Upper Limit
Baseline	1	(none)	1
Week 24	169	2	252
Week 48	337	253	504
Week 96	673	505	840
Week 144	1009	841	1176
Week 192	1345	1177	1512
Week 240	1681	1513	≥1681

Table 3-6. Analysis Visit Windows for Biopsy Data

Analysis Visit	Nominal Day	Lower Limit	Upper Limit
Baseline	1	(none)	1
Week 48	337	169	504
Week 240	1681	505	≥1681

Data relating to unscheduled visits and early termination visits may be assigned to a particular visit or time point based on the visit windows. The following conventions will be followed:

- An unscheduled visit prior to the first dosing of study drug may be included in the calculation of the baseline value, if applicable.
- Unscheduled visits after the first dose of study drug will be included in determining the maximum postbaseline toxicity grade.
- Data collected on a follow-up visit will be summarized as a separate visit, and labeled “Follow-up Visit” for each phase.

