- For baseline, the last available record on or prior to the date of the first dose of study drug will be selected in the corresponding phase. If there are multiple records on the same day, the value with the lowest severity will be selected (eg, normal will be selected over abnormal for safety electrocardiogram [ECG] findings).
- For postbaseline visits, if there are multiple records on the same day, the value with the worst severity within the window will be selected (eg, abnormal will be selected over normal for safety ECG findings).

Postbaseline parameters used to define histology endpoints will be selected in each visit window according to the following rules:

- Histology endpoints including a ≥ 1 -stage improvement in fibrosis without worsening of NASH, progression to cirrhosis, ≥ 1 -stage improvement in fibrosis, NASH resolution without worsening of fibrosis, NAS and elements, SAF and elements will be derived based on parameters collected from 1 biopsy sampling date if the following 4 parameters are available: NASH CRN fibrosis stage, lobular inflammation, hepatocellular ballooning, and steatosis grades.
- When the set of the 4 parameters (NASH CRN fibrosis stage, lobular inflammation, hepatocellular ballooning, and steatosis grades) is available for multiple biopsy samples obtained on different dates in 1 visit window, the set with the biopsy sample collection date closest to the nominal day will be chosen for analysis.. When 2 samples are equidistant from the nominal day, the later set will be selected.
- When the set of the 4 parameters is not complete for any biopsy sample from a single day, the histology endpoints will be derived based on the nonmissing value of each individual parameter closest to the nominal day for that visit window. When 2 records are equidistant from the nominal day, the later record will be selected.
- For Ishak fibrosis stage, the nonmissing value from the biopsy sample collection date closest to the nominal day for the visit window will be selected regardless of the missing status of other parameters. When 2 records are equidistant from the nominal day, the later record will be selected.
- When an endpoint cannot be derived based on all biopsy samples in a visit window, the histology endpoint will be considered missing, and imputation methods listed in Section 3.6.1 will apply.

Liver stiffness by transient elastography data in each analysis visit window will be chosen based on the following rules:

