6.3. Secondary Efficacy Endpoints

6.3.1. Definition of Secondary Efficacy Endpoints

The secondary endpoints of this study are as follows:

- 1) Proportion of subjects who have progression to cirrhosis by Week 48
- 2) Proportion of subjects who have a ≥ 1 -stage improvement in fibrosis (according to the NASH CRN classification) without worsening of NASH at Week 240
- 3) Proportion of subjects who have a ≥ 1 -stage improvement in fibrosis (according to the NASH CRN classification) at Week 48 and Week 240
- 4) Proportion of subjects who have NASH resolution (defined as lobular inflammation of 0 or 1 from at least 1 at baseline and hepatocellular ballooning reduced to 0 from at least 1 at baseline; both criteria are necessary conditions) without worsening of fibrosis (according to the NASH CRN classification) at Week 48 and Week 240

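### A central-read F4 biopsy on Days 2–168 has no analysis window, so it can be scored as no progression to cirrhosis by Week 48

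*SAP*

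**What the plan says.** - **Endpoint.** SAP 6.3.1 lists first among the secondary endpoints: "Proportion of subjects who have progression to cirrhosis by Week 48". Protocol 8.1.4 agrees. SAP 6.3.1 and 6.3.2 give no separate derivation for the cumulative wording.
- **Windows.** In SAP 3.8.2, "Table 3-6. Analysis Visit Windows for Biopsy Data" closes Baseline at Day 1. The next row (analysis visit, nominal day, lower limit, upper limit) reads "Week 48 337 169 504", and Week 240 starts at Day 505. The same section says that all biopsies before OL Study Day 1 will be mapped to Randomized Phase windows.
- **Selection.** SAP 3.8.3 names progression to cirrhosis among the histology endpoints taken from one biopsy date. With several complete biopsies in a window, "the set with the biopsy sample collection date closest to the nominal day will be chosen for analysis". A tie goes to the later one.
- **Nothing usable in the window.** "When an endpoint cannot be derived based on all biopsy samples in a visit window, the histology endpoint will be considered missing", and the imputation methods of SAP 3.6.1 apply.
- **Imputation.** SAP 3.6.1 makes non-responder imputation (NRI) primary for the Week 48 secondary endpoints; under it, "all subjects with missing values will be analyzed as not meeting the corresponding endpoint".
- **Early biopsies.** Protocol 3.3.1 and 6.11.13 provide for a repeat biopsy on clinical suspicion of cirrhosis. Protocol 6.4.6 provides for one at early termination. Both are at the investigator's discretion.
- **After an F4.** Protocol 6.11.13: "If progression to cirrhosis is confirmed by the central reader, the subject will be offered the opportunity to rollover into the OL Phase". Protocol Appendix 2, footnote d, says of liver biopsy: "Not to be performed during the OL Phase of the study". SAP 6 excludes open-label data from efficacy.
- **Event-free survival (EFS).** SAP 6.2.1 counts a central-read F4 biopsy by its onset date, not by visit window.

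**The concern.** For this endpoint, meeting it is the bad outcome. NRI is conservative for fibrosis improvement, but here it turns a missing result into a favourable one. That is a known feature when no biopsy exists. The point here is narrower: a biopsy was taken and centrally read as F4, and the window and selection rules set it aside.

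Two routes lead there. In the first, the F4 falls on Days 2–168 and the subject rolls over. No later biopsy is done, so nothing lies in the Week 48 window. The same loss occurs if the subject stays in the Randomized Phase and the Week 48 biopsy is not F4. In the second, an F4 inside the window is followed by a non-F4 biopsy as close or closer to Day 337. This is possible because rollover is optional. Also, subjects who have permanently stopped study drug cannot roll over (Protocol 6.7) but are encouraged to continue visits (Protocol 6.8).

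At stake are the internal consistency of the report, which could list a subject as a cirrhosis event in EFS and as not progressed by Week 48, and the accuracy of one secondary proportion.

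**Working it through.** No stated figure in the plan rests on this rule, so there is nothing to reproduce. The check applies the rules as written.

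**1. Size of the gap.** From Table 3-6, Day 2 to Day 168 is 168 − 2 + 1 = 167 days, or 167/7 = 23.9 weeks.

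**2. Scenarios.** The SAP column uses Table 3-6, the nearest-to-Day-337 rule (tie to the later biopsy) and NRI. The last column uses the rule under Fix. All biopsies are central reads before OL Study Day 1.

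| Post-baseline biopsies | Biopsy selected for Week 48 | SAP result | With the fix |
|---|---|---|---|
| F4 Day 100 | none; missing, then NRI | not progressed | progressed |
| F4 Day 168 | none; missing, then NRI | not progressed | progressed |
| F4 Day 169 | Day 169 | progressed | progressed |
| F4 Day 100, F3 Day 330 | Day 330 | not progressed | progressed |
| F4 Day 100, F4 Day 330 | Day 330 | progressed | progressed |
| F4 Day 250, F3 Day 330 | Day 330 (7 v 87 days away) | not progressed | progressed |
| F4 Day 250, F3 Day 424 | Day 424 (tie at 87; later wins) | not progressed | progressed |
| F3 Day 330, F4 Day 480 | Day 330 (7 v 143 days away) | not progressed | not progressed |
| F4 Day 480 | Day 480 | progressed | progressed |

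The F4 in every row meets the EFS definition on its own date. The loss is conditional: row 5 shows a gap F4 that does no harm because the selected biopsy is also F4.

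**3. Sensitivity analyses (SAP 3.6.1).** Observed-case analysis drops a subject whose only post-baseline biopsy is in the gap. LOCF might carry the gap F4 forward, but it uses only records eligible for efficacy analysis, and the SAP does not say whether a biopsy with no window is eligible. If it is not, the baseline F3 is carried forward and the subject again counts as not progressed.

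**4. Other endpoints.** EFS uses the onset date and is unaffected. For the primary histology endpoint, a subject with only a gap F4 is missing and becomes a failure under NRI, which is the right answer.

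**5. Size per subject.** With the planned arms (SAP 1.3), one lost F4 moves the placebo proportion by 1/160 = 0.63 points and a SEL arm by 1/320 = 0.31 points. One lost in placebo and one in a SEL arm changes the difference by 0.625 − 0.3125 = 0.31 points.

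**The case against.** The strongest reply is that this will hardly ever happen. No biopsy is scheduled between Screening and Week 48 (Protocol Appendix 2), so a gap biopsy is always discretionary. The blinded snapshot in Protocol 1.2.10 fits that view: of 425 treated, 421 remained on treatment and 3 had stopped study drug, leaving 425 − 421 − 3 = 1 not described. That is not a strict bound, since an F4 subject may decline rollover and the median time on treatment was 11.9 weeks. It does point to few cases, and this objection stands.

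A reader might infer a larger problem from the Phase 2 NASH study (Protocol Table 1-1), where (1 + 2 + 2)/(30 + 27 + 10) = 5/67 = 7.5% had F4 at Week 24. The documents do not support that. Those reads came from scheduled biopsies in a mixed F2–F3 population. Nominal Week 24 is Day 169 in SAP Table 3-4, which is the first day of the Week 48 biopsy window, not part of the gap. Nor is a bias of several points supported. Taking the plan's 30% placebo event rate at 240 weeks and assuming a constant hazard, placebo events of every type by Week 24 come to 160 × (1 − 0.7^(24/240)) = about 5.6. Five gap F4 reads would be nearly all of them, found without a scheduled biopsy.

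For the second route, one can argue that discordant reads reflect sampling or reading variation and that the nearest biopsy is a reasonable choice. That is fair for a status at Week 48. The endpoint is worded as by Week 48, however, and EFS already counts the first F4 whatever follows.

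The consequence is also limited. Secondary endpoints lie outside the testing strategy in SAP 3.5, clinical events are listed by subject, and if SEL slows progression the loss would tend to shrink a benefit rather than create one.

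**Conclusion.** The gap in the derivation is real and follows from the SAP's text. A central-read F4 on Days 2–168 is lost to this endpoint when the selected in-window biopsy is absent or not F4. Less often, an in-window F4 is bypassed. A lone F4 on Day 100 does not count as progression by Week 48, while a lone F4 on Day 480 does.

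It would be too strong to say that every early F4 is lost, or that EFS, the primary endpoint or the trial's error control is touched. The documents give no count of affected subjects. On the visit schedule it is probably very small and may be zero. The effect is 0.63 points per placebo subject and 0.31 points per SEL subject, assuming the planned arm sizes. Severity: minor. It is worth correcting because the change is one sentence and the data already exist.

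**What to change.** For this endpoint only, add to SAP 3.8.3 and 6.3.1:

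*Progression to cirrhosis by Week 48 is any central-read NASH CRN F4 biopsy from Day 2 up to and including the date of the biopsy selected for the Week 48 window (or through Day 168 if no biopsy falls in that window), and before OL Study Day 1. NRI applies only if there is no such F4 and no evaluable Week 48 biopsy.*

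The end date matters. Running the rule to Day 504, the end of the window, would turn a subject with F3 on Day 337 and F4 on Day 480 from correctly not progressed into progressed by Week 48.

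Leave Table 3-6 and the nearest-day rule as they are for the improvement and resolution endpoints. Reconcile the F4 counts with the F4 component of EFS.

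Cost: one SAP sentence and one derivation change, with no new data. There are two downsides. This endpoint will no longer always come from the same single biopsy as the other Week 48 histology endpoints. An early F4 followed by a non-F4 read will count as progression, as it already does in EFS.

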4. SUBJECT DISPOSITION

4.1. Subject Enrollment and Disposition

A summary of subject enrollment will be provided by treatment group and overall for each country and investigator within country. The summary will present the number and percentage of subjects enrolled. For each column, the denominator for the percentage calculation will be the total number of subjects analyzed for that column.

A similar enrollment table will be provided by randomization stratum. The denominator for the percentage of subjects in the stratum will be the total number of randomized subjects. If there are discrepancies in the value used for stratification assignment between the IWRS and the clinical database, the value collected in the clinical database will be used for the summary. A listing of subjects with discrepancies in the value used for stratification assignment between the IWRS and the clinical database at the time of data finalization will be provided.

The randomization schedule used for the study will be provided as a by-subject listing for the CSR.

A summary of subject disposition will be provided by treatment group. This summary will present the number of subjects screened, the number of subjects randomized, and the number of subjects in each of the categories (as applicable) listed below:

- Safety Analysis Set
- Full Analysis Set
- Continuing randomized study drug (for interim analysis)
- Completed randomized study drug
- Did not complete randomized study drug with reasons for premature discontinuation of study drug in the Randomized Phase
- OL Safety Analysis Set
- Continuing OL study drug (for interim analysis)
- Completed OL study drug
- Did not complete OL study drug with reasons for premature discontinuation of study drug in the OL Phase
- Continuing study (for interim analysis)

- Completed study
- Did not complete study with reasons for premature discontinuation of study

For the Randomized Phase, 2 additional categories will be summarized under “Completed study drug”:

- Completed study drug due to protocol-specified clinical events
- Completed 240 weeks of study drug

For the status of study drug and study completion and reasons for premature discontinuation, the number and percentage of subjects in each category will be provided. The denominator for the percentage calculation will be the total number of subjects in the Safety Analysis Set corresponding to that column in the corresponding study phase. In addition, a flowchart will be provided to depict the disposition by study phase.

In the Week 48 interim analysis, subject disposition will be summarized by study phase in 2 tables. The table for the Randomized Phase will be provided by treatment group and include items listed above, except for those based on the OL Safety Analysis Set and the study completion status. The table for the OL Phase will be provided on the OL Safety Analysis Set and will include study drug completion status. The flowcharts also will be provided by study phase.

The following by-subject listings will be provided by subject ID number in ascending order to support the above summary tables:

- Reasons for premature study drug or study discontinuation
- Reasons for screen failure (will be provided by screening ID number in ascending order)
- Lot number and bottle ID

